## 11 Trial schedule and assessments

### 11.1 Overview

Overview of the assessments and procedures applicable to each visit is outlined in [Panel 2](#). Specific details for each assessment and procedure are described in the following sections.

During the course of the trial from screening to the follow-up visit (Week 26/32), unscheduled visits may be needed. It is at the discretion of the investigator to decide which assessments should be performed at an unscheduled visit.

Assessments/procedures at any trial visit must be performed in the following order:

- ePRO: DLQI must be completed by the subject prior to all other trial procedures
- Investigator-blinded assessments (performed only by adequately trained investigators; the same investigator should perform all the evaluations for a given subject throughout the entire trial period)
- Safety and laboratory assessments
- Other assessments and procedures
- ePRO: eC-SSRS and PHQ-8 should be completed by the subject after AE reporting has been completed. Investigator must review the questionnaires and take action, if required, before subject is sent home (see Section [11.4.2](#)).

### 11.2 Assessments performed only at screening/baseline

#### 11.2.1 Demographics

At screening (visit 1) the following demographic details will be recorded:

- Month and year of birth
- Sex
- Race: American Indian or Alaska Native; Asian, Black or African American; Native Hawaiian or Other Pacific Islander; White; Other
- Ethnicity: Hispanic or Latino; Not Hispanic or Latino

#### 11.2.2 Height

The subject's height must be measured in cm (without shoes). The height must be measured using a calibrated meter.

### 11.2.3 Medical history

Relevant past and concurrent medical illness must be recorded based on subject interview. The duration of psoriasis will be recorded (to the nearest whole year).

### 11.3 Concomitant medication and procedures

Use of concomitant medication must be recorded in the subject's medical record and the eCRF (e.g. treatment/drug name, route of administration, total daily dose, indication and dates of start and stop).

For details about previous anti-psoriatic therapy see Section [10.5](#).

### 11.4 Efficacy assessments

#### 11.4.1 Blinded assessments

The blinded assessor must make the following assessments at visits specified in the schedule of trial procedures: PASI, sPGA, BSA and NAPS (see [Panel 2](#)). The assessments will be captured in the eCRF.

The blinded assessor who performs the assessments must be a medically qualified physician trained in the assessments and must remain blinded towards treatment of the subject through the course of the trial. If possible, each subject should have their assessments done by the same assessor throughout the trial. Extra care should be taken to ensure that the same assessor performs the baseline and end of treatment assessments (Week 24), where the co-primary endpoints data is collected. If necessary, trial visits may be rescheduled within the specified window to accommodate when the specific assessor will be available.

The trial site will maintain a written plan detailing which staff members are blinded/unblinded and the process of IMP administration used to maintain the blind.

##### 11.4.1.1 Psoriasis Area and Severity Index (PASI)

The blinded assessor will assess the extent of psoriasis and the severity of the clinical signs (redness, thickness and scaliness) by body region (head and neck, upper extremities, trunk, and lower extremities).

The **extent** of psoriatic involvement will be recorded for each of the four regions (head and neck, upper extremities, trunk, and lower extremities) using the following scale:

**Panel 7 Psoriasis area and severity index – Extent**

Score	Extent of psoriatic involvement
0	No involvement
1	<10%
2	10 - 29%
3	30 - 49%
4	50 - 69%
5	70 - 89%
6	90 - 100%

This assessment of extent is the percentage of that *body region* that is affected and **not** the percentage BSA affected. For example, if one arm was totally affected, and the other arm was totally unaffected, the extent assessment for the arms would be 50% (half of the arms affected).

**Note:**

‘head and neck’ includes head and neck

‘upper extremities’ includes arms and hands

‘trunk’ includes the axilla and groin

‘lower extremities’ includes legs including the buttocks and feet

The **severity** of the psoriasis in each of the four regions (head and neck, upper extremities, trunk, and lower extremities) will be recorded for each of the signs of redness, thickness and scaliness. For each clinical sign, a single score reflecting the average severity of all psoriatic lesions on the given body region will be determined according to the scale below:

**Panel 8 Psoriasis area and severity index – Severity**

Score	Redness
0	None (no erythema)
1	Mild (faint erythema, pink to very light red)
2	Moderate (definite light red erythema)
3	Severe (dark red erythema)
4	Very severe (very dark red erythema)
Score	Thickness
0	None (no plaque elevation)
1	Mild (slight, barely perceptible elevation)
2	Moderate (definite elevation but not thick)
3	Severe (definite elevation, thick plaque with sharp edge)
4	Very severe (very thick plaque with sharp edge)
Score	Scaliness
0	None (no scaling)
1	Mild (sparse, fine scale, lesions only partially covered)
2	Moderate (coarser scales, most of lesions covered)
3	Severe (entire lesion covered with coarse scales)
4	Very severe (very thick coarse scales, possibly fissured)]

Based upon the PASI score at randomisation the investigator must evaluate eligibility, see inclusion criterion 4.

**11.4.1.2 Static Physician’s Global Assessment of disease severity (sPGA)**

The blinded assessor will make a global assessment of the disease severity of psoriasis using the 6-point scale below. This assessment will represent the average lesion severity on the trunk and limbs. The assessment will be based on the condition of the disease at the time of evaluation and not in relation to the condition at a previous visit.

### Panel 9 Static physician’s global assessment of disease severity scale

Score	Short descriptor	Detailed descriptor
0	Clear	No signs of psoriasis; post-inflammatory hyperpigmentation may be present
1	Almost clear	No thickening; normal to pink coloration; no to minimal focal scaling
2	Mild	Just detectable to mild thickening; pink to light red coloration; predominantly fine scaling
3	Moderate	Clearly distinguishable to moderate thickening; dull to bright red, clearly distinguishable erythema; moderate (mild to coarse) scaling
4	Severe	Severe (marked) thickening with hard edges; bright to deep dark red coloration; severe/coarse scaling covering almost all lesions
5	Very severe	Very severe thickening with hard edges; deep dark red coloration; very severe/very coarse scaling covering all lesions

#### 11.4.1.3 Assessment of the body surface area involvement (BSA)

The investigator must first evaluate eligibility of the inclusion criterion for the BSA before evaluating the total psoriatic involvement on the head and neck, upper extremities, trunk, and lower extremities.

The blinded assessor will use the surface area of the subject’s hand (palm and fingers) as a reference measurement to calculate the percentage of each body region that is affected by psoriasis. One hand is approximately equal to 1% total BSA.

Furthermore, the complete body surface area (BSA=100%) can be divided into regions that approximates percentages of BSA as follows: head and neck (10%), upper extremities (20%), the trunk including the axillae and groin (30%), and finally the lower extremities, including the buttocks (40%).

#### 11.4.1.4 Nail Psoriasis Severity Index (NAPSI)

The NAPSI scale is an objective, numeric, and reproducible grading system for nail psoriasis that incorporates the many different features of nail psoriasis. For assessments in this trial (including selection of target nail), a nail is graded using the NAPSI scale by first dividing the nail area with imaginary horizontal and vertical lines into 4 quarters. The following 8 clinical features of nail psoriasis are then scored based on the number of quarters in which the feature is present (0 to 4) to arrive at a NAPSI score of 0 to 32 for each nail:

- pitting
- leukonychia
- red spots in lunula

- nail plate crumbling
- oil drop (salmon patch) discoloration
- onycholysis
- nail bed hyperkeratosis
- splinter haemorrhages

In randomised subjects with nails involved with psoriasis, each nail will be scored at baseline to determine the worst nail (i.e., the nail with the highest NAPSI score). Those subjects whose nail with the highest NAPSI score is 6 or above at baseline visit will have this nail (the target nail) followed for the remainder of the trial. If multiple nails have the same highest score, only 1 target nail will be followed. Subjects whose nail with the highest NAPSI score is 5 or less will not have a designated target nail.

#### **11.4.2 Patient reported outcomes – Efficacy and safety**

The subject must make self-assessments at visits specified in the schedule of trial procedures ([Panel 2](#)).

The following assessments will be done by the subject and must be completed prior to any other procedure at the applicable visit. An ePRO tablet will be provided to the sites for the subject to use when answering the PROs at site.

##### **11.4.2.1 Dermatology Life Quality Index (DLQI)**

The DLQI is a validated questionnaire with content specific to subjects with dermatology conditions ([Finlay and Khan, 1994](#); [Appendix 5B](#)). It consists of 10 items addressing the subject's perception of the impact of their skin disease on different aspects of their quality of life over the last week such as dermatology-related symptoms and feelings, daily activities, leisure, work or school, personal relationships, and the treatment. Each item is scored on a 4 point Likert scale (0 = not at all/not relevant; 1 = a little; 2 = a lot; 3 = very much). The total score is the sum of the 10 items (0 to 30); a high score is indicative of a poor quality of life. The DLQI takes about 2 minutes to complete.

The investigator must evaluate eligibility of the inclusion criterion for the DLQI.

##### **11.4.2.2 Patient Health Questionnaire-8 (PHQ-8)**

The PHQ-8 is a validated and widely used 8 item version of the Patient Health Questionnaire depression scale designed to clinically assess patients for symptoms and signs of depression ([Kroenke et al. 2009](#); [Appendix 5C](#)).

The PHQ-8 takes approximately 3 minutes to complete.

PHQ-8 scores  $\geq 10$  must be reported as an AE and the subject referred to a mental health professional (score  $\geq 10$  is cut-point for defining current depression; [Kroenke et al. 2009](#)). Subjects scoring  $\geq 15$ , corresponding to moderately severe to severe depression, must in addition be withdrawn from the trial, see Section [10.8.1](#).

### **11.4.2.3 Electronic self-rated version, Columbia-Suicide Severity Rating Scale (eC-SSRS)**

The eC-SSRS is a standardized and validated instrument developed for the assessment of the severity and frequency of SIB ([Mundt et al. 2010](#), [Posner et al. 2011](#)).

The eC-SSRS divides SIB into suicidal ideation (level 1-5), suicidal behaviour, and non-suicidal self-injurious behaviour:

#### **Suicidal ideation**

- Level 1: Wish to be dead or not to wake up
- Level 2: Non-specific thoughts
- Level 3: Specific thoughts of method
- Level 4: Some intent to act, no plan
- Level 5: Specific plan and intent

#### **Suicidal behaviour**

- Actual suicide attempts
- Interrupted attempts
- Aborted attempts
- Preparatory actions

#### **Non-suicidal self-injurious behaviour**

- Non-suicidal self-injurious behaviours

The eC-SSRS takes approximately 3 to 10 minutes to complete.

At all visits with scheduled assessment of SIB, using the eC-SSRS, the questionnaire must be filled by the subject after all other visit activities have been completed.

Any positive finding in suicidal ideation of level 4 or 5 or any positive finding in history of suicidal behaviour must be reported as an AE and the subject referred to a mental health professional and withdrawn from the trial, see Section [10.8.1](#).

Documentation of the training and certification must be archived in the investigator trial file. This documentation must be in place before any eC-SSRS results are evaluated by the investigator.

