### Overall rationale for the amendment

The reason for the amendment is to clarify that exclusion criteria related to the PROs eC-SSRS and PHQ-8 pertain to both the screening and the baseline visit. Also, the wording for the eC-SSRS criteria, and the described assessment hereof, has been updated to reflect the report from the eC-SSRS. The wording in eTMF version 3.0 of the protocol was based on the paper version of the C-SSRS.

Substantial changes to the original protocol are provided in the table below. When applicable, original text is cited in quotation marks (‘’) with deletions as ~~strike through~~, additions in **bold**, and descriptive comments in *italics*. Minor editorial revisions have also been applied during this amendment without further indication.

Substantial changes in Amendment 2	Affected Section(s)	Rationale for change
The header versioning (and front page) has been aligned with the eTMF versioning (the electronic archiving system). Hence, with this amendment the header version has been updated from version 2.0 to 4.0.	All sections	To align header versioning with the eTMF versioning.
The “V11” column in the schedule of procedures is now marked “x” for the task “returning fumaric acid esters”.	Panel 2	This was missing by mistake.

TRIAL ID: LP0160-1327	DATE: 17-APR-2018	VERSION: 4.0 PAGE 4 OF 108
-----------------------	-------------------	-------------------------------

Substantial changes in Amendment 2	Affected Section(s)	Rationale for change

12. Any positive finding in history of suicidal behaviour (e.g., ‘actual suicide attempts’, ‘interrupted attempts’, ‘aborted attempts’, or ‘preparatory actions’) based on the eC-SSRS questionnaire at screening or baseline. <del>Subjects with a history of suicidal behaviour.</del>
 
13. Any positive finding in suicidal ideation of level severity 4 or 5 (‘some intent to act, no plan’ or ‘specific plan and intent’) based on the eC-SSRS questionnaire at screening or baseline.
 
14. A PHQ-8 score of <math>\geq 10</math> corresponding to moderate to severe depression at screening or baseline.
	Sections 2, 6.6, 9.3, 11.4.2.2, 11.4.2.3, and Appendix 1	Clarification that exclusion criteria related to the PROs eC-SSRS and PHQ-8 pertain to both the screening and the baseline visit. Also, the wording for the eC-SSRS criteria has been updated to reflect the report of the electronic version of the C-SSRS.

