## 5 Schedule of procedures

### Panel 2 Schedule of trial procedures

Visit	Screening		Treatment phase										Unscheduled visit  or early termination visit 	Follow-up V13 
	V1	V2  Baseline	V3	V4	V5	V6	V7	V8	V9	V10	V11	V12 End of treatment 24/168		
Visit Week/Day	Up to 28 days prior to V2	0/0	1/7	2/14	3/21	4/28	6/42	8/56	12/84	16/112	20/140	24/168		26/182 or 32/224 
Visit window (days) 			± 3	± 3	± 3	± 3	± 3	± 3	± 3	± 3	± 3	± 3		± 3
Trial population and eligibility (Sections 11.2.3 and 11.3)														
Informed consent 	x													
Eligibility criteria	x	x 												
Medical history, incl. concurrent illness	x													
Previous anti-psoriatic therapy	x													
Concomitant medication/procedures	x	x	x	x	x	x	x	x	x	x	x	x	(x)*	x
Other investigator assessments only at screening/baseline (Section 11.2)														
Demographics	x													
Height	x													
Investigational medicinal product and randomisation (Section 10)														
Randomisation		x												
IWRS	x	x						x	x	x	x		(x)	
Handing out IMP:														
Brodalumab		x						x	x	x	x		(x)	
Fumaric acid esters		x						x	x		x		(x)	
Treatment instruction	x 	x 	x 											
Drug accountability/ Treatment compliance			x	x	x	x	x	x	x	x	x	x	(x)*	
Blinded assessments of efficacy Section 11.4.1)														
PASI	x	x	x	x	x	x	x	x	x	x	x	x	(x)*	
sPGA		x	x	x	x	x	x	x	x	x	x	x	(x)*	
BSA involvement	x	x	x	x	x	x	x	x	x	x	x	x	(x)*	
NAPSI		x							x			x	(x)*	

	Screening	Treatment phase											Follow-up	
Visit	V1	V2  Baseline	V3	V4	V5	V6	V7	V8	V9	V10	V11	V12 End of treatment 24/168	Unscheduled visit  or early termination visit 	V13 
Visit Week/Day	Up to 28 days prior to V2	0/0	1/7	2/14	3/21	4/28	6/42	8/56	12/84	16/112	20/140			26/182 or 32/224 
Visit window (days) 			± 3	± 3	± 3	± 3	± 3	± 3	± 3	± 3	± 3	± 3		± 3
Reminders – Continued														
Dispense disposal containers for brodalumab syringes		x												
Handout cooler bag for transport of brodalumab		x												
Subject information folder		x												
Subject to bring ePRO device with them to site visit			x	x	x	x	x	x	x	x	x	x	(x)*	
Review ePRO device answers			x	x	x	x	x	x	x	x	x	x	(x)*	
Subject to return ePRO, disposal containers, and cooler bag to site												x	(x)*	

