1) Subjects must be randomised within 28 days after screening or as soon as all inclusion and exclusion criteria are confirmed. Allow time for results from screening samples to be available from central lab.

2) An unscheduled visit can be performed before the follow-up visit for the following purposes: By individual need at the discretion of the investigator, AE follow-up (and related concomitant medication/procedures, if applicable), re-instructing the subject in procedures for home treatment with the investigational medicinal product, re-collection of blood and/or urine samples in case of medical need of following up on specific test abnormalities, suspicion of pregnancy, or in case of sampling or testing errors necessitating the collection of new samples. Procedures are marked in brackets "(x)" since they are optional depending on the reason for the unscheduled visit.

- 3) Subjects, who are withdrawn from the trial or discontinues trial treatment for any reason, should attend an early termination visit as soon as possible after last dose to have all early termination assessments performed. All mandatory assessments applicable for an early termination visit are marked with an asterix (\*). If a subject discontinues trial treatment or withdraws at a visit, then all mandatory assessments for an early termination visit must be performed at this particular visit.
- 4) Follow-up visit should be conducted no sooner than approximately 5 half-lives after the last administration of investigational medicinal product. Hence,
  - at 8 weeks ( $\pm 3$  days) after Week 24 or early termination visit for subjects allocated to brodalumab; and
  - at 2 weeks ( $\pm 3$  days) after Week 24 or early termination visit for subjects allocated to fumaric acid esters.Additional follow-up visit(s) should be performed only in case an AE is ongoing at the initial follow-up visit and is either a non-serious AE classified as possibly or probably related to investigational medicinal product or an SAE. No data will be collected at the additional follow-up visit(s). Where the (sub)investigator considers it appropriate, any additional follow-up visit(s) may be performed as a telephone contact.

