- 5) All visit-dates should be scheduled relative to the baseline visit, except for the follow-up visit which should be scheduled relative to the date of end of treatment visit (captured at Week 24 or at an early treatment withdrawal visit) and the investigational medicinal product (see note 4).
- 6) Informed consent must be signed both by subject and (sub)investigator (medically qualified) before any trial related procedures are carried out.
- 7) Re-evaluation of in-/exclusion criteria, including review of results from the central laboratory of screening samples.
- 8) At screening, all subjects will receive information that if they are randomised to brodalumab they will have to self-administer the subcutaneous injections. The subjects must confirm that he/she or the subject's designated person will be able to administer the subcutaneous injections that randomisation to brodalumab would entail.
- 9) The 2 first administered brodalumab doses, at baseline and Week 1, should be administered by the subject or designated person at the clinical trial site under supervision of the investigator or delegated person. After Week 1, IMP should be administered at home by subject or the subject's designated person (subcutaneous injection if randomised to brodalumab and oral administration if randomised to fumaric acid esters).
- 10) The DLQI should be completed by the subject prior to all other trial procedures and the electronic self-rated version, columbia-suicide severity rating scale (eC-SSRS) and the patient health questionnaire-8 (PHQ-8) should be completed after all other assessments have been performed.
- 11) Serum beta hCG test must be done in female subjects of childbearing potential (must also be done at visits after screening if a urine test is positive for pregnancy).
- 12) Sodium, potassium, magnesium, bicarbonate, albumin, blood urea nitrogen (BUN), creatinine, uric acid, total bilirubin, direct bilirubin, Alk phosphatase, aspartate aminotransferase (AST), alanine aminotransferase (ALT), and C-reactive protein (CRP).
- 13) RBC (red blood cell count), haemoglobin, haematocrit, platelets, white blood cell count (WBC), and differential (absolute count and %): neutrophils, lymphocytes, monocytes, eosinophils and basophils.
- 14) Specific gravity, pH, occult blood, protein, glucose, leucocyte esterase, ketones, and urine pregnancy test.

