#### Treatment phase (Week 0 to Week 24)

The start of the treatment phase is defined as Week 0 (baseline). At this visit, eligibility will be confirmed by re-checking the eligibility criteria in subjects who were eligible based on previous examinations and the lab results received from central lab for the samples taken at the screening visit. The investigator must ensure that lab values which are used to assess eligibility have been received and reviewed. If still eligible, the subject will continue in the trial and receive a unique randomisation number that determines the application scheme of IMP for the individual subject (see Section [10.3](#)).

Baseline, efficacy, and safety assessments during the trial are described in Section [11](#).

Efficacy assessments are performed by an assessor blinded to treatment.

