## **9 Trial population and withdrawal**

### **9.1 Subject eligibility**

The (sub)investigator must only randomise subjects who meet all eligibility criteria, who are not put at undue risk by participating in the trial, and can be expected to comply with the protocol.

The subject's eligibility for the clinical trial must be checked according to the inclusion and exclusion criteria at the screening visit and the baseline visit.

Any implementation of national requirements/law for the subject's participation in the clinical trial must be ensured and described in the documentation submitted to authorities/ethics committees, as applicable.

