12. Any positive finding in history of suicidal behaviour (e.g., ‘actual suicide attempts’, ‘interrupted attempts’, ‘aborted attempts’, or ‘preparatory actions’) based on the eC-SSRS questionnaire at screening or baseline.
13. Any positive finding in suicidal ideation of level 4 or 5 (‘some intent to act, no plan’ or ‘specific plan and intent’) based on the eC-SSRS questionnaire at screening or baseline.
14. A PHQ-8 score of  $\geq 10$  corresponding to moderate to severe depression at screening or baseline.
15. History of cancer:
  - a. Subjects who have had basal cell carcinoma, localised squamous cell carcinoma of the skin or in situ carcinoma of the cervix are eligible provided that the subject is in remission and curative therapy was completed at least 12 months prior to the date informed consent was obtained.
  - b. Subjects who have had other malignancies are eligible provided that the subject is in remission and curative therapy was completed at least 5 years prior to the date informed consent was obtained.
16. Known or suspected hypersensitivity to component(s) of the IMPs.
17. Current participation in any other interventional clinical trial, ending another interventional clinical trial less than 4 weeks prior to screening visit, or receiving other investigational agents (based on interview of the subject).
18. Subjects who have received treatment with any non-marketed drug substance (i.e. an agent which has not yet been made available for clinical use following registration) within the last 4 weeks prior to screening visit.
19. Previously enrolled in this clinical trial.
20. In the opinion of the (sub)investigator, the subject is unlikely to comply with the clinical trial protocol (e.g. due to alcoholism, drug addiction or psychotic state).
21. Subjects in close affiliation with the trial personnel (e.g. immediate family member or subordinate), subjects being a member of the clinical trial personnel, or being an employee of the sponsor or a CRO involved in the trial.

TRIAL ID: LP0160-1327	DATE: 17-APR-2018	VERSION: 4.0 PAGE 39 OF 108
-----------------------	-------------------	--------------------------------

22. Subjects under guardianship, hospitalised in a public or private institution, for a reason other than the research, or subject deprived of freedom.
23. Female subjects who are pregnant or breastfeeding.

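### At Visit 2 the rule that the eC-SSRS comes after everything else conflicts, read literally, with using it to clear exclusion criteria 12 and 13 before randomisation

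*Combined protocol and SAP*

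**What the plan says.** **Order of the questionnaire.** Section 11.4.2.3 covers all visits with a scheduled eC-SSRS and says "the questionnaire must be filled by the subject after all other visit activities have been completed". Three other places also set an order:

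- Section 11.1 fixes a sequence for any trial visit. The eC-SSRS and PHQ-8 come last, after AE reporting, and the investigator's review is due before the subject goes home.
- Panel 2, footnote 10, places both questionnaires after all other *assessments*.
- The lead-in to Section 11.4.2 places the patient-reported outcomes ahead of any other procedure at the visit.

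**Use of the result.** Criteria 12 (suicidal behaviour) and 13 (ideation level 4 or 5) in Section 9.3 are each "based on the eC-SSRS questionnaire at screening or baseline". Criterion 14 excludes a PHQ-8 score of 10 or more at either visit. The stated purpose of Amendment 2 was to "clarify that exclusion criteria related to the PROs eC-SSRS and PHQ-8 pertain to both the screening and the baseline visit".

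**Eligibility before randomisation.** Section 9.1: "The (sub)investigator must only randomise subjects who meet all eligibility criteria". Section 8.1, on the Week 0 visit: "If still eligible, the subject will continue in the trial and receive a unique randomisation number". Section 10.3.1 says the same. Panel 2, footnote 1: "Subjects must be randomised within 28 days after screening or as soon as all inclusion and exclusion criteria are confirmed". Footnote 7 describes the Visit 2 eligibility step as "Re-evaluation of in-/exclusion criteria, including review of results from the central laboratory of screening samples".

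**What happens at Visit 2.** Panel 2 schedules randomisation, the IWRS call and IMP hand-out at this visit. Section 10.2.1 and Panel 2, footnote 9, add the first brodalumab injection, given on site under supervision.

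**The concern.** A result that decides whether a subject may be randomised cannot be collected after every other activity of the randomisation visit. If a site follows Section 11.4.2.3 as written, a subject who was negative at screening and is newly positive at baseline is found only after allocation and, in the brodalumab arm, after the first injection. Section 6.2.1 names suicidal ideation and behaviour as an important potential risk of brodalumab, and criteria 12 and 13 are there to keep such subjects off the drug.

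The arms differ in exposure. The first fumaric acid ester dose is taken at home that evening (Section 10.2.1), so the review required before the subject leaves still precedes it. The brodalumab dose has no such margin.

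What follows late detection depends on the finding:

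- Suicidal behaviour, ideation level 4 or 5, or a PHQ-8 of 15 or more requires discontinuation (Sections 10.8.1, 11.4.2.2 and 11.4.2.3).
- A PHQ-8 of 10 to 14 meets criterion 14 but triggers no automatic stop. It leads to an AE report and referral (Section 11.4.2.2), and stopping is discretionary (Sections 9.5.1 and 10.8.1). An ineligible subject could stay on treatment.

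Either way the subject remains in the FAS by default, unless removed as a special case under Section 13.2. The Section 13.3.5 sensitivity analysis excludes ineligible subjects randomised in error.

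**Working it through.** This is mainly a check of text against text; the plan has no figure of its own to reproduce.

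**Step 1: same visit.** Section 13.3.10 identifies the randomisation visit as Visit 2 and takes baseline from it. The questionnaire rows of Panel 2 were not readable in the copy reviewed; that the eC-SSRS is due at baseline follows from criteria 12 and 13.

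**Step 2: the two orders at Visit 2.**

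| Source | Order |
|---|---|
| Section 11.4.2.3, read literally | all other activities, including randomisation, hand-out and first brodalumab dose → eC-SSRS |
| Sections 8.1, 9.1 and 10.3.1 with criteria 12 and 13 | eC-SSRS and review → eligibility decision → randomisation → first dose |

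The eC-SSRS cannot come both after and before randomisation.

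**Step 3: do the other timing texts settle it?**

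- Footnote 10 refers to assessments only. It can be met before randomisation, but it does not override the mandatory wording of Section 11.4.2.3.
- Section 11.1 conflicts only if its item for other assessments and procedures is read to include randomisation and dosing. For the PHQ-8, which Section 11.4.2.3 does not cover, the text is therefore ambiguous rather than contradictory. The review deadline in Section 11.1 is departure from the site, not randomisation or dosing.
- The Section 11.4.2 lead-in would avoid the problem, but it is a general sentence that contradicts Section 11.4.2.3. It is not a Visit 2 exception.

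None of these states an exception for Visit 2.

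**Step 4: scale.** Those affected are negative at screening, newly positive at baseline at most 28 days later, and randomised before review. The documents give no rate. For scale only, assume a newly positive rate r with all such subjects randomised before review:

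| r | 204 × r (both arms) | 102 × r (brodalumab arm) |
|---|---|---|
| 0.5% | 1.02 | 0.51 |
| 1% | 2.04 | 1.02 |
| 2% | 4.08 | 2.04 |

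Brodalumab exposure before a mandatory stop is one 210 mg dose, since the next is due on Day 7 (Panel 5).

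A discontinued subject kept in the FAS counts as a non-responder. One such subject moves that arm's response rate by at most 1/102 = 0.98 percentage points; two move it by at most 2/102 = 1.96 points. Allocation is 1:1 and either arm can lose subjects this way, so no direction of bias follows.

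**The case against.** The best defence is that Section 11.4.2.3 cannot be meant literally at any visit. The same section calls for an AE report, referral and withdrawal after a positive answer, and Section 11.1 calls for review and action. On this view, steps that depend on the result are implicitly outside the rule, and at Visit 2 those steps include the eligibility decision, randomisation and first dose. The requirement to confirm eligibility first is explicit and repeated, so the harm arises only if a site breaks several clear rules because of one word, *activities*. A workable order exists: assessments, AE reporting, questionnaires, eligibility decision, randomisation, dose. It satisfies Section 11.1, footnote 10 and the eligibility rules.

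Much of this stands. That order is very likely the intent, many sites would infer it, and the protocol nowhere permits randomising before eligibility is confirmed. Screening has already filtered subjects, discontinuation is mandatory for a positive eC-SSRS, and a sensitivity analysis is prespecified. The assumed rates have no anchor in the documents, and having every such subject randomised before review is a worst case.

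It does not remove the conflict. Review and referral respond to an answer, whereas randomisation and dosing are scheduled parts of Visit 2. That the Visit 2 eligibility re-check also needs the result shows again that the sentence cannot be followed at that visit. Sites are left to infer the exception, with a third order in the Section 11.4.2 lead-in adding to the confusion.

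**Conclusion.** The concern holds. For the eC-SSRS, the mandatory order in Section 11.4.2.3, read literally, is incompatible at Visit 2 with clearing criteria 12 and 13 before randomisation, and no exception is stated. For the PHQ-8 and criterion 14 the text is only ambiguous.

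The case rests on subject safety: a stated instruction, if followed, defeats a safety exclusion for a named potential risk of brodalumab. Its numerical reach is small. The number affected is unknown; about 1 to 4 of 204 randomised, of whom about 0.5 to 2 in the brodalumab arm, is illustrative and depends on the assumed 0.5% to 2% rate and on all being randomised before review. No power or alpha figure changes. It should be corrected, but it does not threaten the primary analysis.

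**What to change.** In Sections 11.4.2.3 and 11.1, state that at Visit 2 the eC-SSRS and PHQ-8 are completed by the subject and reviewed by the investigator after the other assessments and AE reporting, but before the IWRS randomisation and the first IMP dose. Keep the existing order at later visits. Align the Section 11.4.2 lead-in so that it no longer gives a different order for these two questionnaires. Footnote 10 and all thresholds can stay as they are.

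The cost is a wording change in three sections and a notice to sites. No procedure or visit time is added. The eC-SSRS takes 3 to 10 minutes and the PHQ-8 about 3, so 3 + 3 = 6 to 10 + 3 = 13 minutes of existing work is simply placed ahead of randomisation at one visit.
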